3.2 Objectives

We hypothesise that existing cross-sectional imaging (MRE) from the routine NHS care of patients with CD can be used to screen patients for evidence of axSpA, thereby prompting onward referral to the rheumatology department for further management.

The objectives of this study are therefore to determine:

1. the validity, sensitivity, specificity and area under the ROC curve of MRE as a screening tool for axSpA in CD, using dedicated axial MRI scans with clinical assessment as the gold standard.
2. the proportion of patients with evidence of axSpA on MRE imaging who fulfill the 2009 ASAS criteria for axSpA, modified New York criteria for AS and the CASPAR criteria for PsA.
3. the proportion of these patients proceeding to non-pharmacological and pharmacological treatment of their axSpA, as a surrogate measure of change in clinical care as a result of MRE screening.
4. the extra-articular features associated with axSpA in CD, in order to better characterise the clinical phenotype of eSpA.
5. whether the site of CD (colon, ileum, etc.) predicts the occurrence of axSpA.

4. Study design

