consultant musculoskeletal radiologist ([name]) and appropriate onward referrals and communication with the patient will be made.

Prior to the commencement of MRE screening, both scorers will score the same ten MREs to determine inter-rater agreement. Both scorers will then score the same ten MREs on two separate occasions a month apart, to determine intra-rater agreement.

The scoring system for sacroiliac joints on MRE imaging will be divided into two sections as follows:

- i) Joint margins and contour (score range 0 – 2; 0=normal, 1=mildly abnormal, 2=severely abnormal)
- ii) Juxta-articular bone marrow signal (score range 0 – 3; 0=normal, 1=mild, 2=moderate, 3=severe)

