4.3.3 Axial MRI Scan

Non-contrast MRI imaging of the whole spine and sacroiliac joints, using a dedicated protocol including T1 weighted and fluid sensitive sequences, will be performed in both the cases and controls. Images will be reviewed by two independent expert musculoskeletal radiologists ([name] and a colleague musculoskeletal radiologist) and any discrepancies will be decided by consensus agreement. Since MRI review by a second radiologist is not standard of care, it is funded by the research grant for the clinically indicated axial MRI scans. The MRI review by both of the radiologists for the axial MRI scans performed for research purposes is funded by the research grant.

These will be assessed and scored using the spondyloarthritis research consortium of Canada (SPARCC) MRI index criteria which is a validated scoring system for the assessment of spinal and sacroiliac joint inflammation on MRI [43, 44]. To calculate the SPARCC MRI index criteria score for the spine, the six most abnormal discvertebral levels on the STIR sequence are used. At each of the 6 levels, 3 consecutive slices are included and each slice is divided into four quadrants with each quadrant being scored as normal (score 0) or increased signal (score 1). In addition, each slice is scored for intensity and depth of inflammation to give a total possible score of 108 (see Appendix 8). To calculate the SPARCC MRI index criteria score for the sacroiliac joints, six coronal slices of the

sacroiliac joints on the STIR sequence are chosen and each slice is divided into four quadrants. Each quadrant is then scored as normal (score 0) or increased signal (score 1). In addition, each slice is scored for intensity and depth of inflammation to give a total possible score of 72 (see Appendix 9). The SPARCC MRI index criteria has been validated and reported to be the most reliable MRI inflammation scoring system in a number of studies due to its sensitivity to changes and high inter-reader reliability [45-47]. The dedicated MRI scans will also be scored using the specifically designed scoring system as follows:

- i) Joint margins and contour (score range 0 – 2; 0=normal, 1=mildly abnormal, 2=severely abnormal)
- ii) Juxta-articular bone marrow signal (0 – 3; 0=normal, 1=mild, 2=moderate, 3=severe)

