8.2 Statistical analysis

Statistical input has been sought from the University of Cambridge Statistics Clinic (PhD student [name] and his supervisor [name]) and will be supported by [name]. Inter- and intra-rater reliability testing will be performed for the MRE and axial MRI assessments using intra-class correlation coefficients (ICC). The proportion of CD cases with evidence of axSpA on MRE imaging who fulfil diagnostic criteria for axSpA will be expressed as a percentage. Further descriptive analyses will also be performed on study participants. Due to the possible preponderance of patients with axial pain willing to participate in the study and therefore selection bias, we will not be able to calculate the true prevalence of axSpA in CD patients.

As it is expected that the majority of data collected will be count data with an excess of zero-values, a zero-inflated Poisson (ZIP) regression model will be used to test for association between the presence of axSpA, MRE score, PROMs, clinical indices, site of CD and blood biomarkers. In addition, ZIP regression will be used to test for association between MRE scores and those of dedicated axial MRI scans. Zero-inflated binomial regression will be used as appropriate, where the mean approximates the variance. Two-tailed tests will be performed, and the alpha set at 0.05.

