5. Bone marrow signal in the centre of each vertebra constitutes the reference normal signal. If the entire vertebra is abnormal, closest normal level is used for reference. Do not score disc lesions.
6. Each discovertebral level is divided into four quadrants: 1 upper anterior endplate, 2 upper posterior endplate, 3 lower anterior endplate, 4 lower posterior endplate. The presence of increased signal in each quadrant is recorded for each of the 3 sagittal slices. Maximum score is 12 per discovertebral level. Maximum score for 6 levels = 72
7. A score for “intense” may be assigned to each level on each slice. High signal from cerebrospinal fluid acts as a reference for assigning an “intense” reading score to a bone lesion. A score of 1 is assigned if “intense” signal is seen in any quadrant on a single slice. Therefore maximum score per slice is 1, per level is 3 and for 6 levels = 18.
8. A score for “deep” may be assigned to each level on each slice. A lesion is graded as “deep” if there is homogeneous and unequivocal increase in signal extending over a depth of at least 1 cm from the surface of the endplate. A score of 1 is assigned if “deep” signal is seen in any quadrant on a single slice. Therefore maximum score per slice is 1, per level is 3 and for 6 levels = 18.
9. Pre- and post-treatment MR images are scored together with observer blinded to time sequence.

Total maximum score is 108:

Presence of “bone marrow oedema” = 72

Presence of “intense oedema” = 18

Presence of “deep oedema” = 18

Appendix 9: The spondyloarthritis research consortium of Canada (SPARCC): Magnetic Resonance Imaging index for scoring inflammation in the sacroiliac joints[44].

SCORING METHODOLOGY

1. All scores are dichotomous – present or absent, 1 or 0.
2. Only 6 coronal slices are assessed. Slices 4-9 are usually selected as those representing the largest proportion of the synovial compartment of the SI joints. Images scored at a second time point are selected to correspond as closely as possible to the first time point – normally 4-9, 3-8 or 5-10.
3. Only abnormalities on the STIR sequence are scored. T1 SE images are included for anatomical reference.
4. Score all lesions within the iliac bone. Within the sacrum, score lesions medially as far as the lateral border of the sacral foramina.
5. Sacral inter-foraminal bone marrow signal is used as the reference for normal to determine a threshold for increased signal in periarticular bone.

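### Section 8.2 has no rule for over-dispersed counts: its only switch away from ZIP applies where ZIP is already adequate, and no suitable model is named for the binary outcome in objective 5

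*Combined protocol and SAP*

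**What the plan says.** Section 8.2 expects mostly counts with many zeros. On that ground it names ZIP regression for associations among one undivided list of variables: axSpA status, MRE score, patient-reported outcomes, clinical indices, Crohn's disease site and blood markers. It does not say which of these are responses and which are covariates. It adds that "ZIP regression will be used to test for association between MRE scores and those of dedicated axial MRI scans".

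The only alternative model is in this sentence: "Zero-inflated binomial regression will be used as appropriate, where the mean approximates the variance". The testing rule is "Two-tailed tests will be performed, and the alpha set at 0.05". Neither section 8.2 nor any other section names a negative binomial model, a check for over-dispersion, a robust variance or logistic regression.

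Three other places matter:
- Section 3.2, objective 5, asks "whether the site of CD (colon, ileum, etc.) predicts the occurrence of axSpA". That outcome is binary.
- Section 4.2.1 scores MRE on two short grades, 0 to 2 for joint margins and, for marrow, "Juxta-articular bone marrow signal (score range 0 – 3; 0=normal, 1=mild, 2=moderate, 3=severe". Section 4.3.3 applies the same grades to the dedicated MRI.
- Section 4.3.3 and Appendices 8 and 9 also score the dedicated MRI by the SPARCC index, with maximum 108 for the spine and 72 for the sacroiliac joints.

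**The concern.** A rule for leaving ZIP should act when the count part varies more than a Poisson distribution allows. The stated rule acts when mean and variance agree. If negative binomial was intended, the condition points the wrong way. If binomial is meant literally, the model has less variance than a Poisson and cannot absorb over-dispersion. On either reading the analyst has no instruction when variance exceeds mean, and either stays with ZIP or chooses a model after seeing the data.

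At stake are the tests of MRE score against dedicated-MRI score and the predictor analyses. With an over-dispersed response, ZIP standard errors are too small and the stated alpha of 0.05 is not kept. For a yes/no response the fault runs the other way: standard errors are too large and power is lost.

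**Working it through.** Section 8.2 states no figure that depends on the model, so there is none to reproduce. The check has four steps.

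**1. When does the switch act?** Let π be the structural-zero share. Variance/mean ratios are:
- Poisson: 1
- ZIP, whole score, count mean λ: 1 + πλ
- Binomial: 1 − p
- Zero-inflated binomial, maximum n: 1 − p + πnp
- Negative binomial, mean μ: 1 + μ/size

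A ratio of 1 in the count part is the Poisson case, so ZIP is adequate. A ratio of 1 in the whole score would need πλ = 0, in which case plain Poisson would do. A zero-inflated binomial reaches exactly 1 when π = 1/n: 1.4% for n = 72 and 0.9% for n = 108, which does not fit an expected excess of zeros. For the short grades the condition is easier to meet approximately: with p = 0.1 and π from 0 to 0.7, the ratio runs from 0.90 to 1.04 for n = 2 and from 0.90 to 1.11 for n = 3.

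**2. Is over-dispersion likely?** For the spine, section 4.3.3 says "At each of the 6 levels, 3 consecutive slices are included and each slice is divided into four quadrants", and Appendix 8 says "The presence of increased signal in each quadrant is recorded for each of the 3 sagittal slices". A quadrant lesion visible on all three slices therefore scores 3. Intensity and depth each add up to 3 per level ("Therefore maximum score per slice is 1, per level is 3 and for 6 levels = 18"), so a single lesion can score up to 3 + 3 + 3 = 9. If lesions per patient were exactly Poisson and each scored c points, score variance/mean = E[c²]/E[c]:
- every lesion 3 points: 9/3 = 3.0
- every lesion 9 points: 81/9 = 9.0
- equal mix of 1, 3, 6 and 9: 31.75/4.75 = 6.7

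The ratio is 1 only if every lesion scores exactly 1.

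**3. Effect on the test for an over-dispersed response.** Two groups of 66 are taken from section 8.1. Assumed, because the documents do not give them: 50% structural zeros, count mean 8, a null binary covariate, covariate in the count part only, model-based likelihood-ratio test. The approximation 2 × [1 − Φ(1.96/√ratio)] is set beside repeated simulation:

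| Count-part variance/mean | Approximation | Simulated ZIP rejection |
|---|---|---|
| 1 | 5.0% | 4.6–5.6% |
| 2 | 16.6% | 16–18% |
| 3 | 25.8% | 25–27% |
| 9 | 51.4% | 48–50% |

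At ratio 3, simulated rejection is 22% with count mean 4, 24% with 30% structural zeros and 27% with 70%. Scores generated from the SPARCC lesion rules (mean 2 lesions) give 16–20% at 3 points each, 40–41% for the mix and 45% at 9 points each. Across the main simulation set, ZIP with sandwich errors rejects 5.2–7.5%, and choosing ZIP or zero-inflated negative binomial by AIC rejects 4.7–6.7%.

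For short grades the result is different. With 50% structural zeros, ZIP rejects 0.6–2% for a 0–3 item and 1–3.6% for a 0–5 total, below nominal.

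**4. Effect for a binary response.** Fitted to 0/1 data with n = 132, ZIP collapses to plain Poisson (estimated π = 0) and puts 3.6% (prevalence about 30%) to 9.0% (50%) probability on impossible values of 2 or more. The true ratio is 1 − p, so the same approximation gives rejection under the null of 3.4%, 1.9% and 0.6% at prevalence 15%, 30% and 50%. Simulation gives 3.3%, 1.9% and 0.6%. Power, with two groups of 66:

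| axSpA, group 1 v 2 | ZIP, model-based | ZIP, sandwich | Logistic |
|---|---|---|---|
| 20% v 40% | 60% | 72% | 74% |
| 30% v 50% | 43% | 63% | 65% |

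**The case against.** *The response is not stated.* Section 4.3.3 also scores the dedicated MRI on the short bespoke grades and uses SPARCC to validate them. The MRE-against-MRI test may therefore be grade against grade, where ZIP is conservative. This stands. A reader might infer that every association test in section 8.2 has too many false positives; the documents do not support that. The inflation is confined to SPARCC-type or joint-count responses, and objective 5 loses power instead.

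*Zero-inflated binomial is a legitimate model for a bounded grade.* This also stands. A reader might infer that the literal sentence can work only at a structural-zero share of exactly 1/n. But the plan asks only for approximate equality, and step 1 shows that short items with small p meet that over a wide range. The fault is the trigger and the missing over-dispersed option.

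*The error rates rest on assumptions.* They do. The plan does not say whether covariates enter the zero part; with the covariate in both parts, rejection at ratio 3 was 18% against 22% with it in the count part alone, smaller but still inflated. The simulations ignore age and sex matching, and disease site need not split subjects equally. Nine points per lesion is extreme, because lesions at the same level share the intensity and depth points. And since MRE and dedicated MRI image the same sacroiliac joints, no association is implausible there; for that test, understated standard errors matter more than the null rejection rate.

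*It is a wording slip, and statistical support is planned.* Probably so. But correcting it means changing both the model and the direction of the condition, and no other section supplies either.

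**Conclusion.** The concern holds in this form. As written, section 8.2 has no provision for over-dispersed counts, because its one switch is tied to the condition under which ZIP already serves. For SPARCC MRI scores or joint counts as the response, model-based ZIP tests would exceed the stated 5%: about 18%, 25% and 50% at count-part variance/mean 2, 3 and 9. These figures illustrate direction and possible size under the assumptions in step 3; they do not predict this study's results.

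Separately, for occurrence of axSpA the default ZIP is too conservative, with about 60% power against 74% for logistic regression at 20% v 40%.

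A reader might infer that the main result is at risk. It is not: sensitivity, specificity and AUC do not depend on these models. The point should be fixed before analysis, but it concerns the association analyses only.

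**What to change.** Replace the switch sentence in section 8.2 with, for example: *Zero-inflated negative binomial regression replaces ZIP when the count component is over-dispersed after allowing for excess zeros, shown by a lower AIC than ZIP; otherwise ZIP is retained.* ZIP with robust (sandwich) standard errors is an acceptable alternative if chosen in advance.

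Then name the response for each analysis and match the model to it:
- count-type responses (SPARCC MRI index, joint counts, enthesitis count): the rule above
- presence of axSpA, including objective 5: logistic regression
- an MRE grade: ordinal or another bounded-score regression
- continuous patient-reported outcomes or biomarkers (such as BASDAI, ASDAS, CRP): linear regression, transformed if needed

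The cost is wording only, with no new data. In the simulations, zero-inflated negative binomial standard errors were about 2% larger than ZIP's with no over-dispersion (0.090 v 0.088). They were about 1.7 times as large at variance/mean 3 (0.151 v 0.088) and 3.0 times at 9 (0.267 v 0.089), close to the width that a valid 5% test needs.

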8.3 Missing data

If a subject is uncertain how to complete an outcome measure questionnaire correctly, a research professional will be present to provide support and ensure correct and full completion.

9. Ethical considerations

The study will be performed in accordance with the recommendations guiding ethical research involving human subjects adopted by the 18th World Medical Assembly, Helsinki, Finland, 1964, amended at the 52nd World Medical Association General Assembly, Edinburgh, Scotland, October 2000. Informed written consent will be obtained from the patients prior to registration into the study.

Any treatments prescribed for patients within the study who have a diagnosis of axSpA will be in accordance to existing local and clinical commissioning group (CCG) treatment pathways, and will not in any way favour the funder's (MSD) product, namely golimumab (Simponi; an anti-tumour necrosis factor alpha product).

The study will be submitted for approval by the local Research Ethics Committee (REC) via the Integrated Research Application System (IRAS). Ethics approval from the (institutional review board) research and development department of CUH NHSFT will also be sought.

The right of a patient to refuse participation without giving reasons will be respected. The patient will remain free to withdraw at any time from the study without giving reasons and without prejudicing his/her further treatment.

10. Statement of indemnity

Cambridge University Hospitals NHSFT is able to provide insurance to cover for liabilities and prospective liabilities arising from negligent harm. Insurance cover is not provided for claims arising from non-negligent harm. Clinical negligence indemnification will rest with the CUH NHSFT under standard NHS arrangements.

11. Safety

[figure not shown]
Venepuncture is the only potential risk to patients in this study. The healthcare professionals performing this procedure are trained in venepuncture and will also be able to deal with any potential complications. There are no other significant potential risks from the study procedures.

12. Costings

The study will be funded by MSD (Merck, Sharp and Dohme corporation) who have committed £147,273 for the study. This will fund [name] salary for the 24 months of the study, research axial MRI scans, research blood tests and stool sampling, consultant radiologist time to review the dedicated axial MRI scans twice, statistical support and office ancillaries.

13. Appendices

Appendix 1: Study Flow Chart

Appendix 2: Schedule of Procedures

Procedure	Timeline / visits			
	Months 0-6	Months 7-12 (screening/ baseline)	Months 13-18 (follow-up)	Months 19-24
Patient consent for MRE image review and recruitment	●			
MRE training and scoring	●			
Systematic literature review	●			
Demographics		●	●	
Medical history		●	●	
Clinical examination		●	●	
PROMs		●	●	
Blood tests as per standard of care or research		●	●	
'Research' tests (blood and stool samples)		●		
Faecal calprotectin as per standard of care or research		●	●	
Dedicated axial MRI as per standard of care or research, with two expert scorers		●		
Statistical analysis			●	●
Write-up of MD thesis and associated papers				●

Appendix 3: Gantt Chart for the Research Timeline

Task	Mar-Nov 2018	Dec 2018-Feb 2019	Mar 2019-Feb 2020	Mar 2020-Aug 2020
1				
2				
3				
4				
5				
6				
7				
8				

[figure not shown]
Task:

1. Study setup: Protocol and Ethics approval
2. Systematic literature review (on prevalence of axial spondyloarthritis in patients with Inflammatory Bowel Disease based upon cross-sectional imaging)
3. Magnetic Resonance Enterography (MRE) score training and reliability exercise
4. Patient consent for MRE imaging review and recruitment (including control group)
5. Scoring of MRE scans
6. Clinical review of patients in spondyloarthritis clinic including completion of patient reported outcome measures and investigations
7. Statistical analyses
8. Thesis and publication of results

Appendix 4: List of sequences for the MRE protocol at Cambridge University Hospitals NHSFT

MRE Sequence	Fat Suppressed
2D CORONAL FIESTA	No
2D AXIAL FIESTA	No
2D CORONAL SLAB MRCP	No
CORONAL SSFSE	No
CORONAL SSFSE FS	Yes
CORONAL DWI B=600	No
CORONAL FIESTA MULTI Dynamic	No
CORONAL 3D LAVA FLEX GAD	Yes
AXIAL 3D LAVA FLEX GAD	Yes

Appendix 5: Assessment of spondyloarthritis international society (ASAS) criteria for classification of axial spondyloarthritis (to be applied in patients with chronic back pain and age at onset of back pain < 45 years) [50].

Appendix 6: Modified New York Criteria for the diagnosis of ankylosing spondylitis [15].

Requires radiological criterion & ≥ 1 clinical criterion

Radiological criterion

Sacroiliitis grade ≥ 2 bilaterally or grade ≥ 3 unilaterally

Clinical criterion

1. Inflammatory low back pain & stiffness $\geq 30m$ that improves with exercise and is not relieved by rest
2. Reduced motion of the lumbar-spine in both sagittal & frontal planes
3. Limited chest expansion

(having excluded spinal fracture, intervertebral disc disease & fibromyalgia.)

Appendix 7: Classification Criteria for Psoriatic Arthritis (CASPAR) [23].

To meet the CASPAR (CIAssification criteria for Psoriatic ARthritis) criteria, a patient must have inflammatory articular disease (joint, spine, or enthesal) plus ≥ 3 points from the following 5 categories:

1. Evidence of current psoriasis, a personal history of psoriasis, or a family history of psoriasis.

Current psoriasis is defined as psoriatic skin or scalp disease present today as judged by a rheumatologist or dermatologist.

† A personal history of psoriasis is defined as a history of psoriasis that may be obtained from a patient, family physician, dermatologist, rheumatologist, or other qualified health care provider.

A family history of psoriasis is defined as a history of psoriasis in a first- or second-degree relative according to patient report.

2. Typical psoriatic nail dystrophy including onycholysis, pitting, and hyperkeratosis observed on current physical examination.

3. A negative test result for the presence of rheumatoid factor by any method except latex but preferably by enzyme-linked immunosorbent assay or nephelometry, according to the local laboratory reference range.

4. Either current dactylitis, defined as swelling of an entire digit, or a history of dactylitis recorded by a rheumatologist.

5. Radiographic evidence of juxtaarticular new bone formation, appearing as ill-defined ossification near joint margins (but excluding osteophyte formation) on plain radiographs of the hand or foot.

(The CASPAR criteria have specificity of 98.7% and sensitivity of 91.4%)

(† Current psoriasis is assigned a score of 2; all other features are assigned a score of 1.)

Appendix 8: The spondyloarthritis research consortium of Canada (SPARCC): Magnetic Resonance Imaging index for scoring inflammation in the spine[43].

SCORING METHODOLOGY

1. All scores are dichotomous – present or absent.
2. After scanning the entire spine, 6 discovertebral levels are selected for scoring. These levels are chosen as representing the 6 most abnormal levels on the STIR sequence. Levels scored at a second time point are the same as those on the first.
3. After selecting levels, three consecutive sagittal slices are chosen for scoring at each level representing the most abnormal slices for that level.
4. Only abnormalities on the STIR sequence are scored. T1 SE images are included for anatomical reference.
5. Bone marrow signal in the centre of each vertebra constitutes the reference normal signal. If the entire vertebra is abnormal, closest normal level is used for reference. Do not score disc lesions.
6. Each discovertebral level is divided into four quadrants: 1 upper anterior endplate, 2 upper posterior endplate, 3 lower anterior endplate, 4 lower posterior endplate. The presence of increased signal in each quadrant is recorded for each of the 3 sagittal slices. Maximum score is 12 per discovertebral level. Maximum score for 6 levels = 72
7. A score for “intense” may be assigned to each level on each slice. High signal from cerebrospinal fluid acts as a reference for assigning an “intense” reading score to a bone lesion. A score of 1 is assigned if “intense” signal is seen in any quadrant on a single slice. Therefore maximum score per slice is 1, per level is 3 and for 6 levels = 18.
8. A score for “deep” may be assigned to each level on each slice. A lesion is graded as “deep” if there is homogeneous and unequivocal increase in signal extending over a depth of at least 1 cm from the surface of the endplate. A score of 1 is assigned if “deep” signal is seen in any quadrant on a single slice. Therefore maximum score per slice is 1, per level is 3 and for 6 levels = 18.
9. Pre- and post-treatment MR images are scored together with observer blinded to time sequence.

Total maximum score is 108:

Presence of “bone marrow oedema” = 72

Presence of “intense oedema” = 18

Presence of “deep oedema” = 18

Appendix 9: The spondyloarthritis research consortium of Canada (SPARCC): Magnetic Resonance Imaging index for scoring inflammation in the sacroiliac joints[44].

SCORING METHODOLOGY

1. All scores are dichotomous – present or absent, 1 or 0.
2. Only 6 coronal slices are assessed. Slices 4-9 are usually selected as those representing the largest proportion of the synovial compartment of the SI joints. Images scored at a second time point are selected to correspond as closely as possible to the first time point – normally 4-9, 3-8 or 5-10.
3. Only abnormalities on the STIR sequence are scored. T1 SE images are included for anatomical reference.
4. Score all lesions within the iliac bone. Within the sacrum, score lesions medially as far as the lateral border of the sacral foramina.
5. Sacral inter-foraminal bone marrow signal is used as the reference for normal to determine a threshold for increased signal in periarticular bone.
6. Each SI joint is divided into four quadrants: 1 upper iliac, 2 lower iliac, 3 upper sacrum, 4 lower sacrum. The presence of increased signal in each quadrant is recorded. Maximum score for two SI joints in each coronal slice is 8. Maximum score for 6 coronal slices = 48.
7. A score for “intense” may be assigned to each SI joint on each slice. High signal from slow flowing venous blood within presacral veins acts as a reference for assigning an “intense” reading score to a bone lesion. A score of 1 is assigned if “intense” signal is seen in any quadrant of an SI joint on a single slice. Maximum score per slice is therefore 2, and for 6 slices = 12.
8. A score for “deep” may be assigned to each SI joint on each slice. A lesion is graded as “deep” if there is homogeneous and unequivocal increase in signal extending over a depth of at least 1 cm from the articular surface. A score of 1 is assigned if “deep” signal is seen in any quadrant of an SI joint on a single slice. Maximum score per slice is therefore 2, and for 6 slices = 12.
9. Pre- and post-treatment MR images are scored together with observer blinded to time sequence.

Total maximum score is 72:

Presence of “bone marrow edema” = 48

Presence of “intense edema” = 12

Presence of “deep edema” = 12

14. References

1. Stolwijk, C., et al., *Epidemiology of spondyloarthritis*. *Rheum Dis Clin North Am*, 2012. **38**(3): p. 441-76.
2. Sheehan, N.J., *The ramifications of HLA-B27*. *J R Soc Med*, 2004. **97**(1): p. 10-4.
3. Jadon, D.R., et al., *Axial Disease in Psoriatic Arthritis study: defining the clinical and radiographic phenotype of psoriatic spondyloarthritis*. *Ann Rheum Dis*, 2017. **76**(4): p. 701-707.
4. Ozgul, A., et al., *Effect of ankylosing spondylitis on health-related quality of life and different aspects of social life in young patients*. *Clin Rheumatol*, 2006. **25**(2): p. 168-74.
5. Ward, M.M., et al., *Impact of ankylosing spondylitis on work and family life: comparisons with the US population*. *Arthritis Rheum*, 2008. **59**(4): p. 497-503.
6. Healey, E.L., et al., *Ankylosing spondylitis and its impact on sexual relationships*. *Rheumatology (Oxford)*, 2009. **48**(11): p. 1378-81.
7. Tillett, W., C. de-Vries, and N.J. McHugh, *Work disability in psoriatic arthritis: a systematic review*. *Rheumatology (Oxford)*, 2012. **51**(2): p. 275-83.
